5.5 Primary Endpoints

• Ending the vital functions of the patient (medically accepted ex)

Or

- Gloskow Coma Level 13 and above,
- At least 3 days body temperature must have remained normal (measurement from the ear 37.5 C)
- Respiratory symptoms should be significantly improved
- The nucleic acid test must be negative in 2 consecutive tests for the respiratory pathogen (sampling interval must be more than 24 hours)
- Obvious healing of lesions with CT
- There should be no comorbidity or complications requiring hospitalization
- Without oxygen support SaO2 should be> 93%

All of its items have been realized

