5.6 Secondary Endpoints

- Hypersensitivity
- Temporary shortness of breath
- Rarely, redness of the skin is due to heat
- Edema
- Bleeding
- Embolization
- Hematoma
- Hyperpigmentation
- Ache
- paresthesia
- Superficial thrombophlebitis
- May cause urticaria or ulcers.
- Vascular rupture and perforation
- Visible scratch
- Iatrogenic injury may damage the surrounding tissues.
- Hemothorax or pneumothorax.
- Neighboring Nerve Damage Iatrogenically
- phlebitis
- Skin Burn or discoloration

If two or more adverse effects from the above adverse effects are seen, the study is terminated.

6. Statistical Evaluation:

- According to the course of the clinical trial, if we reach the research arm (100 patients), control group (100 patients), the efficacy and safety of the treatment will be examined and an interim report will be prepared. According to the results of the interim report, the clinical trial will be terminated or the clinical trial will be continued until the number of volunteers (400 in total) mentioned above is completed.
- In this interim analysis, the patients completing the study will be evaluated considering the primary and secondary endpoints stated in the protocol and the criteria are as follows:

1-Duration in intensive care

2-Survival rate

Contribution of UVC and laser beam application to the treatment of 3-COVID 19 infection and / or superinfections accompanying COVID 19 infection

The tests to be applied are as follows:

1-Difference test between two averages for intensive care stay

(Mann-Whitney U test or t test) will be used.

2-Survival analysis tests will be used for survival rate.

Accompanying 3-COVID 19 infection treatment and / or COVID 19 infection

To investigate the contribution of UVC and laser beam application to the treatment of superinfections

Chi-square test will be applied.

Descriptive statistics will also be given for demographic data.

REFERENCE STUDIES ABOUT THE APPLICATION OF UVC BEAM "in vitro, in vivo and ex vivo"

1. The Effect of UV-C Ray Reducing Pathogen Rate on Blood Platelets Apps;

Auto-immune diseases HIV 1 -2
T-lymphotropic virus types 1 and 2
Hepatitis B (HBV)
Hepatitis C (HCV)
Hepatitis A and E
Blood pathogens (Treponema pallidum)
Parvovirus B19

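### Primary endpoint joins death and full recovery by Or, with no assessment day and no rule for deaths before recovery; no single primary variable is designated

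*Combined protocol and SAP*

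**What the plan says.** Section 5.5, Primary Endpoints, opens with death: "Ending the vital functions of the patient (medically accepted ex". The word Or follows, then seven recovery items: coma score, temperature, respiratory symptoms, two negative nucleic acid tests, CT healing, no condition needing hospital care, and oxygen saturation without support. It closes with "All of its items have been realized". The only times given are inside items: a three-day run of normal temperature and a gap of more than 24 hours between nucleic acid samples. No assessment day appears, and nothing is said about patients who die before recovering.

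Section 6, Statistical Evaluation, plans an interim report "if we reach the research arm (100 patients), control group (100 patients". It says: "In this interim analysis, the patients completing the study will be evaluated considering the primary and secondary endpoints stated in the protocol". It then lists three criteria: time in intensive care, survival rate, and contribution to treating COVID-19 and/or superinfection. The tests follow: Mann-Whitney U or t test for intensive care stay; "2-Survival analysis tests will be used for survival rate"; and chi-square "To investigate the contribution of UVC and laser beam application to the treatment of superinfections", with COVID-19 treatment named beside it.

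The aims in Section 1.0 name mortality first, with intensive care time and viral load by PCR. The visit schedule in Section 5.4 runs from Day 0 to Day 5, with follow-up at Days 7 and 15. Neither follow-up day is tied to Section 5.5.

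**The concern.** A primary endpoint should fix one variable, one day, one favourable direction and one analysis before data are seen. This one can be read in three ways.

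1. **One composite.** Death and full recovery are then the same event. Turning deaths into recoveries leaves the rate unchanged, and a rise can mean harm or benefit.
2. **Two endpoints**, as the plural heading suggests. The death limb has a family of tests but no day. Recovery has no linked test, no day and no handling of deaths.
3. **A rule for when observation ends.** Items such as "There should be no comorbidity or complications requiring hospitalization" resemble discharge criteria. No primary variable is then designated, and any of the three Section 6 criteria could be called primary afterwards.

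Under each reading, something that determines the trial's main conclusion is left open until the data are known.

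**Working it through.** **Text check.** Each Section 6 test, set against Section 5.5:

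| Section 6 test | Variable | Match in Section 5.5 |
|---|---|---|
| Mann-Whitney U or t test | Intensive care stay | None |
| Survival analysis, test not named | Survival rate | Death limb; no day |
| Chi-square | Contribution to treatment, undefined | Possibly recovery; no variable, day or cross-reference |

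The plan gives no event rate, effect size, significance level or power for any endpoint, so there is no planned figure to reproduce. What follows is illustration.

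**Inputs.** Sizes per arm are 25 (Section 1.0, in figures), 100 (the interim in Section 6) and 200 (half of the 400 in Section 6). All death and recovery rates are assumed, as is a two-sided 5% level. Two-proportion results are for the Pearson chi-square without continuity correction, by exact binomial enumeration. Survivors-only results come from 400,000 simulated trials per case. Percentages are control v device; triplets are 25 / 100 / 200 per arm.

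**Reading 1, one composite.** Let D be the death rate and R the recovery rate; the event rate is D + R. If a share x of patients moves from death to recovery, the rate is (D − x) + (R + x) = D + R, whatever x is. This needs no assumed rate.

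- Deaths 40% v 20%, recoveries 30% v 50%: composite 40 + 30 = 70% v 20 + 50 = 70%. Rejected in 5.4% / 5.1% / 5.0% of trials. Mortality alone, on the same patients: power 35.2% / 88.0% / 99.3%.
- Harm, with deaths 40% v 60% and recoveries 30% v 20%: composite 70% v 80%.
- Benefit, with deaths 40% v 35% and recoveries 30% v 45%: composite also 70% v 80%. Both are rejected in 13.5% / 37.1% / 63.9% of trials, so the result cannot tell them apart.

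**Reading 2, recovery on its own.** In all randomised patients, with deaths counted as not recovered, the rate is R. In survivors only it is R / (1 − D). Take deaths 40% v 20%, so 20% of patients are averted deaths, and control recovery 30%.

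| Averted deaths that recover | All randomised | Survivors only |
|---|---|---|
| None | 30% v 30% | 0.30/0.60 = 50% v 0.30/0.80 = 37.5% |
| A quarter | 30% v 35% | 50% v 0.35/0.80 = 43.75% |
| Half | 30% v 40% | 50% v 0.40/0.80 = 50% |

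- None recover: a survivors-only test finds the device significantly worse in 11.6% / 31.7% / 55.5% of trials although deaths are halved. A difference is created.
- Half recover: the all-patient test has power 12.5% / 31.6% / 55.8%; the survivors-only test rejects in about 5%. A difference is removed.
- A quarter recover: the direction changes.

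**Sensitivity of the first case.** With recovery 10% in both arms, survivors-only is 16.7% v 12.5% and the device is significantly worse in 5.8% / 10.7% / 16.9%. With deaths 60% v 40% and recovery 20% in both arms, it is 50% v 33.3% and 13.7% / 38.8% / 65.7%.

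**The case against.** The best defence is that the plan never proposes to analyse death or recovery as one event. The heading is plural, mortality leads the aims, and Section 6 tests survival separately. Taken separately, death and recovery have obvious directions. Section 6 also says the primary endpoints will be considered, and chi-square would suit a yes/no recovery outcome.

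Much of this stands, and it limits the point. A reader might infer that the primary endpoint has no analysis at all. That is not supported, because survival analysis covers the death limb. Nor do the documents say that the tests apply only at the interim: the criteria are introduced for it, but the list of tests carries no such restriction. The pooled and survivors-only analyses are illustrations of what the text leaves open. Section 6 limits the interim to patients completing the study without saying whether those who died count as completers; that does not amount to a survivors-only plan.

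A reader might also infer that the handling of deaths generally reverses the recovery result. In the cases above it creates or removes a difference, and changes the sign only in some of them.

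What the defence does not supply is a day, a rule for deaths before recovery, a defined variable for the chi-square, or a statement of which criterion is primary. Survival may well be intended, but intensive care stay is listed ahead of it in Section 6.

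**Conclusion.** The point holds and must be fixed before analysis. Section 5.5, followed literally, counts death and full recovery as the same event. Read more generously, it leaves recovery without a linked test, day or handling of deaths, leaves the death limb without a day, and designates no single primary variable.

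The conclusion about the composite is algebraic and rests on no assumed rate. The sizes do rest on assumptions: about 5% rejection against 35% / 88% / 99% power for mortality, and a device wrongly found worse in about 12% / 32% / 55% of survivors-only tests (6% / 11% / 17% to 14% / 39% / 66% under the other rates tried). They show what the open choices could do, not what the sponsor plans to do.

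**What to change.** Replace the Or endpoint with one directional primary variable in all randomised patients, at a fixed day counted from randomisation, with one named test. Analyse the other limb separately.

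The option closest to the documents is all-cause mortality through Day 15, the last scheduled visit, by log-rank. Full recovery at Day 15 would be secondary, with deaths counted as not recovered, by chi-square. The day should be counted explicitly from randomisation because the note under the schedule ties the Day 7 and Day 15 serum samples to clinical improvement.

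A three-level ordinal outcome (dead; alive with items unmet; all seven met) by Wilcoxon is an acceptable alternative. Power under assumed rates, at 25 / 100 / 200 per arm (Wilcoxon from 200,000 simulated trials per case):

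| Assumed effect | Mortality (chi-square) | Ordinal |
|---|---|---|
| Deaths 40% v 20%, all averted deaths recover | 35% / 88% / 99% | 40% / 93% / over 99% |
| Same deaths, half recover | 35% / 88% / 99% | 25% / 74% / 96% |
| Same deaths, none recover | 35% / 88% / 99% | 15% / 45% / 73% |
| Deaths 40% v 35%, recoveries 30% v 45% | 7.5% / 11% / 18% | 13% / 37% / 64% |

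The choice is the sponsor's. Mortality does not count deaths after Day 15 and has little power if the benefit is mainly in recovery.

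The cost is protocol and SAP wording, no extra patients, and vital status at Day 15 for every randomised patient, including those discharged or not completing. If recovery at Day 15 is used, its definition must be reconciled with the schedule:

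- **Temperature.** The item reads "At least 3 days body temperature must have remained normal (measurement from the ear 37.5 C", but after Day 5 vital findings are scheduled only at Days 7 and 15.
- **CT healing.** The imaging note in Section 5.4 accepts a chest film in place of CT.
- **Nucleic acid tests.** Samples fall on Days 1, 3, 5, 7 and 15. On scheduled samples, a negative pair ending at Day 15 also needs a negative at Day 7, so a patient first negative after Day 7 cannot qualify.
- **Respiratory improvement and CT healing.** Neither has a threshold; each needs an operational criterion fixed before data are seen.

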1.0 SUMMARY of INVESTIGATION

Study Title:	Prospective, Parallel, Multicenter Randomized Controlled Study Investigating the Effects of UVC Beam and Laser Beam Therapy According to Standard Therapy in Patients with Covid-19 Diagnosis
Study Code:	MD2020/001
Device :	Turkishbeam Model Number: 1007-001
	*: The device was produced by RD GLOBAL ARASTIRMA GELISTIRME SAĞLIK ILAÇ INSAAT YATIRIMLARI A.S.
Device Classification:	Class III
Purpose of the Study:	Clinical research study that evaluates the effect of Turkish Beam- Selective UV developed by RD GLOBAL ARASTIRMA GELISTIRME SAĞLIK ILAÇ INSAAT YATIRIMLARI A.S. use into Intravascular, Intrapulmonary, Intratracial, Intrarespiratory area. Bacteria, Fungal and Virus-based pathogens systematically to collect and evaluate specific clinical performance and safety data. In our Clinical Research, we aimed to investigate the effectiveness of the treatment group and control group mortality rates, intensive care hospitalization times, monitoring the virus load by PCR, and the treatment effectiveness of UVC

Scope of the Study:	This Clinical Research covers determining the treatment effectiveness and reliability of UVC application to patient groups, the details of which are determined in the protocol.
Application:	Intravascular, Intrapulmonary, Intratracial, Intrarespiratory UVC and Laser Therapy System
Overall Study Design:	Prospective, Parellel, Multicenter, Randomized Controlled
Number of volunteers:	50 patient- 2 groups with 25 (two hundred) patients in each group
Treatment Groups:	Test: Antiviral + Antimalarial + Antibiotic Treatment + UVC Therapy Control: Antiviral + Antimalarial + Antibiotic Treatment
Groups of Volunteer:	Those who are between the ages of 40-75 and who have applied to the clinic with symptoms such as fever, weakness, cough, and shortness of breath, or who have signs of COVID-19 (SARS- CoV-2) test positive or atypical pneumonia findings in CT findings and accepted as COVID 19 infection, and patients undergoing intubation treatment in intensive care unit
Sensitive population / Vulnerable subjects:	The study will not include under-40, pregnant women and those with suspected pregnancy, previously diagnosed with mental disorders, puerperant women and lactating women

Duration of the clinical trial: 3 months (04.2020- 07.2020)

Researched Medical Condition:

and Disease

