According to ICD 10 coding; B34.9 Virus infection is not defined, B34.2 CORONA VIRUS INFECTION UNDEFINED B97.2 Colon virus, causative agent of diseases classified in other sections B97 Viral agents, the cause of diseases classified in other sections B99 infectious diseases, other and unspecified A49.9 bacterial infection not defined

Manufacturer of the Device:

RD Global Arastirma Gelistirme Sağlık Ilaç Insaat Yatirimlari A.S.

Ethics Committees:	Gaziantep University, Klinik Arastirmalar Etik Kurulu
IKU Statement:	This study will be conducted in accordance with the principles of Good Clinical Practice (IKU), the Declaration of Helsinki and the requirements of the legal documents published on this subject.
Privacy:	The name of the Clinical Research Coordinator, Responsible Researcher and Assistant Researcher will be included in the reports. The names of the patients will be kept Confidential. Patient datas will be used by assigning CODE to each patient. Data privacy will be ensured under the "KVKK" (PDPL-Personal Data Protection Law). Identification information / personal identifier of the volunteers such as Patient card, Patient diary will be collected or accessed.
	It will be ensured that the relevant person to be researched has a written consent based on adequate information about the nature and results of the research and that this consent is not dependent on any benefits. Responsible / assistant researchers will receive relevant written commitment on ethics, confidentiality and "PDPL" on this issue.

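### At least two recovery items are undefined judgements with no masking described; reading coded images without the arm would reduce the resulting bias at little cost

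*Combined protocol and SAP*

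**What the plan says.** **Endpoint (section 5.5).** The primary endpoint is death, or recovery defined by a list that closes with "All of its items have been realized". Several items carry a cut-off: coma score 13 or above, ear temperature of 37.5 C for at least 3 days, two consecutive negative nucleic acid tests more than 24 hours apart, and "Without oxygen support SaO2 should be> 93" per cent. Two items carry none: "Respiratory symptoms should be significantly improved" and "Obvious healing of lesions with CT". A further item, "There should be no comorbidity or complications requiring hospitalization", also rests on a clinician's decision.

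**Design and arms (section 1.0).** The design is given as "Prospective, Parellel, Multicenter, Randomized Controlled", and the arms as "Test: Antiviral + Antimalarial + Antibiotic Treatment + UVC Therapy Control: Antiviral + Antimalarial + Antibiotic Treatment". Section 5.4.1 describes intravascular and intrarespiratory catheter application in the research arm. No sham, blinding or masked assessor is described.

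**Imaging (section 5.4, follow-up programme and the notes below it).** Images are scheduled on day 0, day 2, day 5 and at the follow-up visits on days 7 and 15. They may be chest X-ray, CT or both, with clinical judgement as the fallback for patients who cannot be imaged. The notes name three CT features to look for: consolidation, ground glass and reticulo-nodular opacity. Application time in the airway is set from the trachea diameter on CT.

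**Codes (section 1.0, Privacy).** "Patient datas will be used by assigning CODE to each patient".

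**Analysis (section 6).** Patients who complete the study are evaluated against the endpoints. The listed criteria are intensive care duration, survival, and the contribution of UVC and laser to treatment. The last is tested by chi-square, with no variable defined.

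**The concern.** Other items in the same list have numeric limits, so the two unanchored ones stand out. A patient who meets everything else is classed as recovered or not on someone's impression of symptoms and of the images. Control patients have no catheter procedure, so the staff forming that impression can be expected to know the arm. Section 4.8 also records a firm expectation that survival will improve under the treatment. If the same clinical picture is judged a little more generously in one arm, the recovery proportions differ with no treatment effect. A larger sample does not dilute such a difference; it makes it easier to declare significant.

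**Working it through.** **Inputs from the documents.** The all-items rule and the list of items come from section 5.5. The sizes considered are 25 per arm (section 1.0, where the words in brackets say two hundred), 100 per arm (the interim report in section 6) and 200 per arm (half of the 400 in section 6). The plan states no alpha, power, event rate or effect size, so it has no figure of its own to reproduce.

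**Assumptions.** Two-sided alpha of 0.05, uncorrected chi-square, no true treatment effect, and recovery (yes/no) as the variable tested. The recovery rates and pass rates below are not in the documents.

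**Step 1: how unequal judgement reaches the endpoint.** Let *o* be the share of patients who meet all the other items, the same in both arms, and *s* the share of those who pass the judged items.

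Observed recovery = *o* × *s*

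False difference = *o* × (*s* in test − *s* in control)

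With *s* = 70% in control and 90% in test:
- *o* = 0.3: 0.3 × 0.20 = 6 points
- *o* = 0.5: 0.5 × 0.20 = 10 points
- *o* = 0.7: 0.7 × 0.20 = 14 points

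With 80% against 90%, the difference is 3, 5 and 7 points. The false difference can never exceed *o*. A rise from 40% to 50% needs *o* of at least 0.5, and at exactly 0.5 every such patient in the test arm must pass (0.5 × 1.0 = 0.50).

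**Step 2: chance of a significant result with no true effect.** This is the sum, over all pairs of binomial counts, of the probability of those pairs for which the chi-square exceeds its 5% critical value.

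| Observed recovery, control v test | 25 per arm | 100 per arm | 200 per arm |
|---|---|---|---|
| 40% v 40% (no bias) | 6.0% | 5.1% | 4.8% |
| 40% v 45% | 7.9% | 11.6% | 17.0% |
| 40% v 50% | 13.1% | 31.0% | 52.1% |

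At 25 per arm the excess over the no-bias rate is 7.9 − 6.0 = 1.9 points for a 5-point shift, and 13.1 − 6.0 = 7.1 points for a 10-point shift.

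**Step 3: other values of *o*.** With pass rates of 80% v 90% and *o* from 0.3 to 0.7, the false-positive rate is 6.1% to 9.3% at 25 per arm, 7.6% to 17.6% at 100 and 10.5% to 29.2% at 200. With 70% v 90% it is 8.4% to 19.7%, 16.7% to 53.0% and 29.0% to 80.7%.

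**Step 4: what masked image reading can reach.**
- Healing item: covered where there is a CT to read. CT is not required for every patient, and the fallback is clinical judgement.
- Symptom item: not covered, so it needs a separate analysis.
- Hospitalization item: not covered.
- SaO2 item: the value is measured, but when a patient is assessed off oxygen is a care decision taken with the arm known.

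**The case against.** The strongest reply is that the all-items rule limits the harm. Leniency on one item does nothing for a patient who is febrile, still test-positive or dependent on oxygen. Death, the other primary event, cannot be judged leniently. Section 6 does not say that recovery is tested at all, and at 25 per arm the excess error is small. All of this stands, and it is why the figures are conditional illustrations.

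Four stronger readings are tempting, and the documents do not support them.
- A reader might infer that coded image reading removes the bias. Step 4 shows that it cannot.
- A reader might infer that the remedy certainly needs no extra staff. Staffing for outcome assessment is not described. Because CT also sets application time in the test arm, the person who measures the trachea for treatment may know the arm, and deleting the arm from the request would not mask that person. The patient code is there for privacy; nothing says that it hides the arm.
- A reader might want to replace the symptom item with the entry figure for respiratory rate, 30 or above. SaO2 is already a separate item, the patients are intubated so the rate may reflect the ventilator, and anyone who enters below 30 would pass unchanged.
- A reader might say that the protocol declares the trial open-label. It does not. Knowledge of the arm is inferred from the catheter procedures and the absence of any described masking.

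**Conclusion.** The point holds as a low-cost improvement. At least two mandatory recovery items are unanchored judgements, no masking is described, and only one arm has catheter procedures. A component of the primary endpoint is therefore open to a false difference among patients who meet all the other items.

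The size is modest at 25 per arm and potentially large at the 100 or 200 per arm that section 6 still implies. It rests on an assumed 40% recovery rate, assumed shifts of 5 or 10 points, an assumed 5% level, and recovery being what the chi-square tests. The documents do not show that such a shift would occur, or how large it would be.

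**What to change.** 1. Have the person who already reads the scheduled images judge the healing item from images labelled only with patient code and visit, without the arm. That person should neither deliver the UVC treatment nor measure trachea diameter for it. The reading should use the CT features already named in the notes to the follow-up programme.
2. As a sensitivity analysis, report recovery with the symptom item left out, built on the measured items and the masked image reading. State whether the hospitalization item stays in; if it does, that part remains exposed.
3. State in the report that patients without CT, the hospitalization item and the timing of SaO2 off oxygen remain open to knowledge of the arm.

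The cost is removing the arm from imaging requests and one added analysis. No sham and no extra visit are needed. It assumes that each site has an image reader who is not treating the patient, which the documents do not state and the sponsor should confirm.

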5.4 Applied Treatment

5.4.1. Treatment Definition and Method

The system should be inserted into the Invamed Steerable Catheter (disposable CAMERA CATHETER) via an ultraviolet / laser light source and the fiberoptic cables connected on it. Ultraviolet / laser light from the end of the fiberoptic system destroys microorganisms (including viruses) at the end of a second-long application. The system is based on the basis of the elimination of microorganisms in these areas with a low dose of UV light / laser application from the catheter by sending it directly to the body cavities via a fresroptic catheter, intrarespiratory, intravascular (used with intracat). With the help of Invamed Steerable Catheter (Disposable Camera Catheter), UVC beam applied with a catheter inserted into the lungs and accompanying fiberoptic are interventions related to the reduction or elimination of infection. With the application of ultraviolet light / laser beam, the patient is treated with a significant reduction / destruction of the microorganism and inflammation burden in the patient's body. The proposed treatment is an antimicrobial treatment strategy, and it is recommended to combine supportive treatments with this process in terms of a holistic treatment strategy based on the clinical course of the disease. UVC and Laser application will be performed on the research arm, together with intravascular and intrarespiratory application.

Effective Dose: The blood / tissue infected with microorganism, the effective dose required to destroy the microorganism population: 2 mj / cm2 [4]

5.4.1.1. Intravascular UVC Application Process Steps:

- Hands are washed in accordance with the "Hand Hygiene and Glove Directions for Use".
- The patient is given a position in which he / she can feel comfortable according to the application area.
- A protective cover is placed under the interference area.
- Sterile Gloves are worn. IV cannula outer cover is opened.
- Fiberoptic catheter system is slowly pushed into the IV cannula.
- Approximately 5 cm cut from the tip of the catheter is adjusted to remain in the intrvascular area and UVC application is started.
- The Fiberoptic catheter is with drawn slowly after UVC administration at the specified time and strength.
- In order to apply the energy required for microorganism inactivation with the power value applied with UVC source, 200 mj / cm2 energy should be applied for 30 minutes +/- 5 minutes.

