- The patient is given 100% oxygen for 2 minutes,
- Sterile gloves are worn,
- Steerable catheter is advanced through the airway to the orotracheal region in accordance with the aseptic technique.
- Fiberoptic UVC is advanced through the line catheter in accordance with the aseptic technique.
- When the catheter inserted through the nose or mouth reaches the pharynx, the patient is coughed and the catheter is advanced in the inspiratory phase and UVC is applied.
- The patient is monitored throughout the procedure,
- After the procedure, the patient is given 100% oxygen for 1 minute.
- The time required for the tracheal application of the energy required for the microorganism inactivation with the power value applied by the UVC source, these values are indicated in the table below according to the trachea diameter. (Table 1).

Respiratory Application Diameter Mm	Power Per Unit Area	Application time	Energy Required
Diameter (mm)	mw/cm ²	S	mj/cm ²
5	67,90	2,95	200
10	61,11	3,27	200
15	57,72	3,47	200
20	55,00	3,64	200
25	52,28	3,83	200
30	49,57	4,03	200
35	46,85	4,27	200
40	44,14	4,53	200
45	42,10	4,75	200
50	40,74	4,91	200
	(Table	1)	

Depending on the trachea diameter in the drawn CT, force should be applied for the time specified in the relevant table. The amount of energy to be transferred to the tissue is arranged according to the table with each advance of the fiberoptic catheter 1 cm.

The healthcare personnel who receive the treatment, taking into consideration the clinical condition of the patient, should not exceed the maximum application time (30 min \pm 5 min in intravascular applications, 5 min \pm 1 min in intrarespiratory applications), and this should be at most 5 days. should apply in accordance with the protocol.

CLINICAL WORK TREATMENT AND FOLLOW-UP PROGRAM								
Evaluation	Screening Visit (Day 0)	Inclusion / Randomization (Day 0)	Treatment Visit (Day 1)	Treatment Visit (Day 2)	Treatment Visit (Day 3)	Treatment Visit (Day 4)	Treatment Visit - Final (Day 5)	Label Period / Follow-up Visit (Day 7&15)
Informed Volunteer Consent Form	Х							
Demographic information	X							
Medical history / General physical examination	X	X	X	X	X	X	X	x
Current treatments (drugs)	X	X	x	x	X	X	X	
Biochemistry, Complete blood count	X	X	x	x	X	X	X	x
Radiological Imaging	X	X		X			X	X
Vital findings	X	X	X	X	X	X	X	X
Include / exclude criteria		X	X	X	Х	X	X	
Pregnancy test (serum / urine)	X	X						
randomization		X						
Dose diary			X	X	X	X	X	

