Adverse Event		X	X	X	X	X	X	X
Concomitant Therapy (UVC)			x	x	x	X	x	x
PCR sampling			X		X		X	X
Serum Antibody Level			1					X

Following the improvement of the clinical course of the patients, it is planned to take the patient's serum plasma on the 7th and 15th days, and to test and store it under suitable conditions for the antibody test.

Blood tests to be performed: Complete blood count, urea, creatinine, sodium, IL-1 β , IL-6, TNF α , TGF β potassium, chlorine, AST, ALT, total bilirubin, LDH, CPK, D-dimer, troponin, Ferritin, fibrinogen, procalcitonin, CRP values, quantitative measurement of PCR results of the source of infection

Radiological Imaging: Chest X-ray and / or Lung CT is taken. Clinical decision should be made according to history and examination findings in patients who cannot have chest X-ray and / or lung CT. (Radiological findings: Consolidation, ground glass appearance and reticulo-nodular opacity

appearance should be investigated in lung CT. Signs of pneumonia in lung graphy should be examined.)

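### The recovery endpoint requires healing on CT, but the imaging rule allows chest X-ray alone, so patients followed as the protocol permits can recover and still not count; a bias towards UVC is possible but its size is unknown.

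*Combined protocol and SAP*

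**What the plan says.** Section 5.5 makes the primary endpoint either death or a list of seven recovery conditions, closed by "All of its items have been realized". One condition is "Obvious healing of lesions with CT". The section names no comparison scan or time point for healing, and does not say how to score a condition that was not assessed.

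The follow-up table in section 5.4.1 schedules imaging on Day 0 (screening and inclusion), Day 2, Day 5, and Days 7 and 15. The note under it reads "Radiological Imaging: Chest X-ray and / or Lung CT is taken", with a fallback: "Clinical decision should be made according to history and examination findings in patients who cannot have chest X-ray and / or lung CT". Neither sentence distinguishes the arms.

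The airway steps in section 5.4.1 (b and c) use CT for another purpose: "Depending on the trachea diameter in the drawn CT, force should be applied for the time specified in the relevant table". Those steps belong to one arm: "UVC and Laser application will be performed on the research arm, together with intravascular and intrarespiratory application".

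CT is not compulsory at entry. Sections 1.0 and 5.1 accept a positive test as an alternative to CT findings, and the imaging criterion in section 5.2 accepts either X-ray or tomography.

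**The concern.** Two stated rules conflict. The endpoint can be met only with a CT, while the schedule is satisfied without one. A patient who recovers on every clinical condition and is imaged by X-ray at each visit has complied with the protocol, yet cannot be counted as recovered. This affects both arms and makes the recorded recovery rate too low.

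The second issue is whether the loss is equal between arms. Healing is a change, so judging it on CT normally needs an earlier CT. The airway procedure gives research-arm patients a reason to have one, and no trial procedure does the same for controls. If controls more often lack the earlier scan, and a missing CT counts as failure, the recorded recovery rates differ even when UVC has no effect.

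**Working it through.** **Step 1: the two rules side by side.** Recovery requires all seven items, one of them on CT. Imaging requires X-ray and/or CT. Take a patient imaged only by X-ray: the imaging rule is met, the CT item has no data, and the literal result is not recovered. No assumption about arms is needed. If a share f of patients has a usable follow-up CT in both arms and true recovery is r, recorded recovery is r × f. With r = 30% and f = 50%, that is 0.30 × 0.50 = 15%.

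**Step 2: inputs for the arm comparison.** The plan gives no alpha, sidedness, power or recovery rate, so it has no figure of its own to reproduce. The following are assumptions:
- true recovery r = 30% in both arms (no treatment effect);
- a missing CT is scored as failure;
- every UVC patient has an earlier CT, and a share q of controls does not (20%, 30%, 50%);
- a share f of both arms has follow-up CT (50%, 70%, 100%);
- CT availability is unrelated to recovery, and earlier and follow-up availability are unrelated to each other;
- the recovery composite is compared by an uncorrected chi-square test at two-sided 5%.

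Both 25 and 200 per arm are shown because the documents give both: 25 per group in figures in section 1.0, and 400 in total in section 6.

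**Step 3: formulas.** Recorded recovery is r × f in the UVC arm and r × f × (1 − q) in controls. For f = 100% and q = 20%: 30% against 0.30 × 0.80 = 24%. For f = 50% and q = 20%: 15% against 0.15 × 0.80 = 12%. The chance of a significant result favouring UVC is the sum of the exact binomial probabilities of all tables that reject in that direction.

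**Step 4: results** (q = 20% / 30% / 50%).

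| Follow-up CT, both arms | UVC recorded | Control recorded | False result for UVC, 25 per arm | False result for UVC, 200 per arm |
|---|---|---|---|---|
| 50% | 15% | 12 / 10.5 / 7.5% | 5 / 7 / 13% | 14 / 27 / 67% |
| 70% | 21% | 16.8 / 14.7 / 10.5% | 6 / 9 / 18% | 19 / 38 / 83% |
| 100% | 30% | 24 / 21 / 15% | 7 / 11 / 26% | 27 / 54 / 95% |

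The nominal value in that direction is about 2.5%.

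**Step 5: sensitivity.** With equal CT availability (100% in both arms, or 70% in both), the rate favouring UVC is 2.5% to 3.2% at either size for r of 30%, 50% or 70%: no inflation, only under-counting when CTs are missing. With f = 100% and 25 per arm, higher true recovery enlarges the effect. At r = 50% it is 12.6 / 21.4 / 47.9%, and at r = 70% it is 19.1 / 36.1 / 75.5%.

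**The case against.** A reader might infer that, because only the UVC procedure calls for a CT, controls will fail the endpoint for want of a scan and UVC will look better with no effect. The documents do not support that as a conclusion, for these reasons:

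- The CT in the airway steps is read before exposure, to find an application time. The endpoint turns on a later scan, which is optional in both arms. A UVC patient followed by X-ray fails the item just as a control does.
- The sizing CT may be one already taken. Imaging is scheduled at screening, before randomisation, so CTs from that visit should be balanced. The national guide reproduced in section 4.6 calls for lung CT in certain fever-and-cough presentations regardless of arm, so many controls may have an admission CT.
- Section 5.5 names no comparison scan, so the need for an earlier CT is itself an inference.
- Scoring a missing CT as failure is the literal reading, but no rule says so. If sites accept X-ray or clinical judgement instead, the bias could shrink, vanish or reverse.
- Section 6 names intensive care stay, survival, and the contribution of UVC to treatment (chi-square). It does not define the recovery composite as the chi-square outcome, and survival does not depend on CT.

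All of this stands against the size of the bias, and some of it against its direction. None of it removes the conflict between sections 5.5 and 5.4.1. Three answers remain. The guide is background text, applies only to some presentations, and elsewhere accepts a chest radiograph for pneumonia. Informal substitution of judgement would leave a primary endpoint to unwritten discretion in a trial whose documents describe no blinding. And section 6 does say that the interim evaluation considers the primary endpoints, so the composite is not idle.

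**Conclusion.** The conflict is certain and needs correcting: as written, a patient followed by X-ray under the protocol cannot meet the recovery limb in either arm. The under-count equals the share of truly recovered patients without a usable CT, which the documents do not give.

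The bias towards UVC is possible, not shown. It requires that controls more often lack an earlier CT, that a missing CT counts as failure, and that the composite is tested between arms. Under those assumptions and 30% true recovery, the illustrative false-positive rate in favour of UVC runs from 5% to 26% at 25 per arm and from 14% to 95% at 200 per arm. The upper ends assume follow-up CT in every patient and no earlier CT in half the controls. These figures show that the item is sensitive to unequal scanning; they do not estimate what would happen in this trial.

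**What to change.** Reword the item as clear resolution or reduction of lesions on the same modality (chest X-ray or CT) as the patient's Day 0 screening image, with that modality recorded before randomisation. Then add:

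- A CT taken only to size the trachea for UVC is not used for the endpoint unless the Day 0 modality was CT.
- A patient with no lesion at Day 0 meets the item if none is seen at assessment.
- One rule, identical in both arms, covers a patient with no Day 0 image or no follow-up image.
- The clinical-decision fallback in section 5.4.1 does not score this item.

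Reading the images without knowledge of arm would strengthen the item further. Section 6 should also say whether and how the recovery composite is compared between arms.

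The core change is to wording and adds no scans, provided follow-up imaging uses the recorded modality. The downsides are that X-ray is a coarser measure of healing than CT, and that the endpoint mixes modalities across patients. Because modality is fixed before randomisation, that mix should be balanced between arms.
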